## 10. EFFICACY

### 10.1. Analysis of the primary efficacy criterion

The primary objective will be analysed by performing a t-test (or a Wilcoxon test if the normality assumption is not acceptable) on the means of AUC of total WURSS-21 score during first eight days of symptoms between treatment groups.

The answers of the twenty first items of the WURSS-21 questionnaire are scored from 0 to 7 (0: negative answer; from 1 to 7: positive answer with an increasing severity level). See the daily symptom report in appendix (§13.3).

The total WURSS-21 score at each time point is the sum of the scores of the twenty first items of the WURSS-21 questionnaire:

$$\text{At each time point } t: \text{WURSS}_{\text{TOT}}(t) = \sum_{j \in \{1; \dots; 20\}} \text{WURSS}_j(t)$$

AUC of total WURSS-21 score will be computed by the method described in §6.4.7.

At time points the questionnaire has been completed, possible unanswered items will be imputed by the method described in §6.4.6.

Subjects will be analysed on the Full Analysis Set and the Per-Protocol Set. In each case, boxplots of the AUC on total score will be realized by treatment group. The number of available data and the p-value will be printed on the figure.

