#### 7.1.3 Primary Endpoint with methods and timing for assessing recording and analysing variables

**The AUC of Wisconsin Upper Respiratory Symptom Survey (WURSS-21) during first 8 days of symptoms will be compared between both groups.**

WURSS-21 is a validated 3-dimensional structure questionnaire [12]. This survey has been demonstrated to be responsive, and valid to assessing the severity and functional impact of the common cold. It includes 10 items assessing symptoms (symptoms score, (items 2 to 11), 9 items assessing functional impairments (quality of life score, (items 12 to 20).) and 2 items assessing respectively global severity and global change. Brown et al. [13] support the practice of using, for AUC computation, a simply summed daily global illness severity score to represent the overall symptomatic and functional impairments arising from acute upper respiratory infection.

The WURSS-21 will be assessed in an e-diary once daily in the evening, taking into account the symptoms from the morning to the evening, during D2-D8 (day of the end of treatment). At D1, the WURSS-21 will be completed during the visit. After D8, the WURSS-21 will be assessed once daily until the subject feels not sick for two consecutive days.

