#### Visit 1 (V1) - (Day 1): Screening/Inclusion/Randomization

Subjects with symptoms of acute infectious rhinitis for  $\leq 48h$  will go to the site for the screening/inclusion visit (visit 1). The investigator will give oral information relative to the study and will answer all questions relative to the study participation. The patient will receive the information sheet. If the subject agrees to participate in the study, he/she will be asked to give a written consent.

Each screened subject will be assigned a subject identifier number during screening that will be used on all subject documentation. The subject identifier number will contain the site number and the subject number and will be assigned in numerical order at the screening visit based on chronological order of screening dates (e.g., 001-010 for the 10th subject screened at the Site #001).

The investigator or his/her delegated designee will:

- Record demographic data, medical history and ongoing medication.
- Perform a physical and clinical examination. A pharyngeal nasal swab will be performed by the investigator or by the delegated study nurse to check for absence or presence of SARS-CoV2.
- Verify that eligibility criteria are fulfilled.
- Record the score of the common cold symptoms (headache, muscle ache, chilliness, sore throat, blocked nose, runny nose, cough, sneezing according to a physician-rated symptom score after clinical examination; (scale: 0  $\rightarrow$  3 [0: no symptom, 1 = mild symptoms (sign/symptom clearly present, but minimal awareness; easily tolerated), 2 = moderate symptoms (definite awareness of sign/symptom that is bothersome but tolerable), 3 = severe symptoms (sign/symptom that is hard to tolerate; causes interference with activities of daily living and/or sleeping]). This scoring system was developed by Jackson in 1958 and is widely used in common cold clinical trials [14].
- Review and detail the question of the WURSS-21.
- Allocate a treatment number for eligible subjects via the eCRF.
- Explain how to complete every day the e-diary for WURSS-21 recording, how to report concomitant medications, adverse events/incidents/expected undesirable side effects. The patient will access the e-diary application using a smartphone.

*NB: The first WURSS-21 will be completed by the subject on site during this visit after the randomization of the patient.*

- Remind the patient to return the device for assessment of compliance to the treatment at V2.

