**Strictly Confidential**

possible malfunction before the patient leaves the site. In case of dysfunction, a new randomisation number and a new treatment will be attributed to the patient using the eCRF back-up randomisation module.

*NB: The first use of the device will be performed in the evening of the Day 1.*

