### **8.3 Primary endpoint**

For the primary criterion analysis, AUC for the WURSS-21 will be compared between Healsea® Rescue\* group and Placebo group using a Student's t-test. If the usual applicability assumptions for the Student's t-test are not met, a Mann-Whitney test will be used.

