**Figure 1 : Flow chart of the study**

## 4. SAMPLE SIZE

A sample of 180 subjects (90 subjects per group) will be needed to provide 80% power with a one-sided test at a 0.05 significance level to detect a difference between Healsea® Rescue\* and Placebo groups AUC of 30%.

Assuming that approximately 10% of subjects may drop-out the study, 200 subjects will be randomly assigned at a ratio 1:1 to Healsea® Rescue\* and Placebo (100 subjects per group).

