### 6.3. Statistical/Analytical issues

#### 6.3.1. Significance level

All statistical analyses will be performed at the 0.05 global significance level (type I error rate), using one-sided tests.

The statistical results are conclusive for the primary efficacy criterion.

All the other statistical results have to be considered within a descriptive perspective and not as inferential issues. No adjustment for Type I error is done. P-values of statistical tests will be provided for information only.

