### 10.2. Analysis of the secondary efficacy criteria

#### 10.2.1. AUC for each of the WURSS-21 components (symptoms and Quality-of-Life)

For the symptoms' and Quality-of-Life's scores of the WURSS-21 questionnaire, the AUC will be computed by the method described in §6.4.7 and a t-test (or a Wilcoxon test if the normality assumption is not acceptable) will be performed on the means of AUC during first eight days of symptoms between treatment groups.

The symptoms' WURSS-21 score at each time point is the sum of the items 2 to 11 of the WURSS-21 questionnaire:

$$\text{At each time point } t: \text{WURSS}_{\text{symptoms}}(t) = \sum_{j \in \{2; \dots; 11\}} \text{WURSS}_j(t)$$

The Quality-of-Life's WURSS-21 score at each time point is the sum of the items 12 to 20 of the WURSS-21 questionnaire:

$$\text{At each time point } t: \text{WURSS}_{\text{QoL}}(t) = \sum_{j \in \{12; \dots; 20\}} \text{WURSS}_j(t)$$

At time points the questionnaire has been completed, possible unanswered items will be imputed by the method described in §6.4.6.

Subjects will be analysed on the Full Analysis Set and the Per-Protocol Set. In each case, boxplots of both AUC on symptoms' and Quality-of-Life's scores will be realized by treatment group. Numbers of available data and p-values will be printed on the figure.

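### The primary AUC comparison does not adjust for the pre-treatment Day 1 WURSS-21 score: the test is valid, but it gives up precision by an amount the documents do not fix

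*SAP*

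**What the plan says.** SAP 10.1 sets out the primary analysis: "The primary objective will be analysed by performing a t-test (or a Wilcoxon test if the normality assumption is not acceptable"), applied to the AUC of the total score over the first eight days. Protocol 8.3 names Student's test and adds that if the assumptions of the "t-test are not met, a Mann-Whitney test will be used". The symptom and quality-of-life AUCs are handled alike in SAP 10.2.1: "a t-test (or a Wilcoxon test if the normality assumption is not acceptable) will be performed on the means of AUC". No covariate appears in any of these analyses, and neither document plans a baseline-adjusted sensitivity analysis.

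The timing of the D1 score is given in the protocol. Section 7.1.3 says: "At D1, the WURSS-21 will be completed during the visit". Section 7.4.1, under Visit 1, says: "The first WURSS-21 will be completed by the subject on site during this visit after the randomization of the patient". It also says: "The first use of the device will be performed in the evening of the Day 1". The D1 score is therefore recorded after allocation but before any exposure, in a blinded trial.

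SAP 6.4.7 calculates the AUC by the trapezoidal rule from D1 to D8 and sets it to missing if D1 is missing. SAP 8.5 describes the baseline total score and tests it between groups. That is its only other use.

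**The concern.** A severity score measured before treatment usually predicts severity over the following week. When it does, a comparison that leaves it out carries between-subject variation that could have been removed. Here the score is already collected, and every subject with an AUC has one, so adjustment would lose no analysed subject and would cost one degree of freedom. The baseline test in SAP 8.5 does not recover the lost precision.

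What is at stake is the power of a single test. SAP 6.3.1 says: "The statistical results are conclusive for the primary efficacy criterion"; all other p-values are descriptive. SAP 4 says the planned sample "will be needed to provide 80% power with a one-sided test at a 0.05 significance level", so the margin for lost precision is modest.

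**Working it through.** **Inputs from the documents.** 90 evaluable subjects per group, one-sided alpha 0.05, 80% power, a 30% difference in AUC, 10% dropout and 200 randomised (SAP 4, protocol 8.5). Trapezoidal AUC from D1 to D8 (SAP 6.4.7).

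**Not given, so assumed.** The SD and placebo mean of the AUC, and the correlation ρ between the D1 score and the AUC.

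**Step 1: the plan's own figures.** 180/(1 − 0.10) = 200, which matches. The figure of 180 cannot be derived forwards without an SD, so I solve backwards for the standardised effect d:

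- Normal approximation: d = (1.645 + 0.842) × √(2/90) = 0.371.
- Noncentral t: d = 0.372.
- If 30% means 30% of the placebo mean, SD/mean = 0.30/0.372 = 0.81.

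**Step 2: t-test branch.** ANCOVA multiplies the residual SD by √(1 − ρ²), so the effective d is 0.372/√(1 − ρ²), with 177 degrees of freedom at 90 per group. For example, at ρ = 0.5 the variance factor is 0.75, the effective d is 0.372/0.866 = 0.430, and power is 89.0%.

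| Assumed ρ | Variance factor 1 − ρ² | Power, 90 per group | Power, 100 per group |
|---|---|---|---|
| none (unadjusted) | 1 | 80.0% | 83.6% |
| 0.1 | 0.99 | 80.3% | 83.9% |
| 0.2 | 0.96 | 81.4% | 84.9% |
| 0.3 | 0.91 | 83.2% | 86.5% |
| 0.5 | 0.75 | 89.0% | 91.7% |
| 0.7 | 0.51 | 96.7% | 97.9% |

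**Step 3: what ρ might be.** D1 has weight 0.5 in an AUC whose weights are 0.5, six 1s and 0.5. With independent days of equal variance, ρ = 0.5/√(0.25 + 6 + 0.25) = 0.20. With equal variances and a day-to-day correlation of 0.3 to 0.7, ρ is 0.28 to 0.52 under a first-order autoregressive pattern and 0.56 to 0.84 under compound symmetry. These are models, not trial data. The entry limit of a symptom score no higher than 9 (protocol 7.3.1), although on another scale, may narrow D1 severity and lower ρ.

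**Step 4: Wilcoxon branch.** This branch may well operate: a normal AUC with SD/mean 0.81 would put Φ(−1/0.81), about 10.7%, of subjects below zero, which is impossible for this score. I simulated a skewed (lognormal) AUC with that SD/mean, 90 per group, and a 23.6% reduction chosen so that Wilcoxon has about 80% power. Rank ANCOVA then gave 81%, 82% and 88% at rank correlations of 0.19, 0.28 and 0.48.

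**Step 5: rank or raw scale?** Power with a 30% reduction, at latent correlations of 0.2, 0.3 and 0.5:

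| Assumed shape | Wilcoxon | Rank ANCOVA | Raw-scale ANCOVA |
|---|---|---|---|
| Lognormal | 95% | 96%, 96%, 98% | 92%, 92%, 95% |
| Gamma | 84–85% | 86%, 87%, 92% | 92%, 92%, 96% |

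Neither scale wins for both shapes.

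**Step 6: validity.** With normal data and ρ of 0.3, 0.5 and 0.7 (4,000 trials each), the rejection rate under no effect was 5.5%, 5.0% and 5.3% for the unadjusted t-test and 5.4%, 4.7% and 5.3% for ANCOVA. In gamma and lognormal checks (40,000 trials) the t-test, Wilcoxon test and both ANCOVAs gave 4.8% to 5.3%.

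**The case against.** The strongest reply is that nothing here is an error. Protocol and SAP agree, neither promises adjustment, and an unadjusted test in a 1:1 single-site trial is a legitimate choice. That stands: this is a point about efficiency, not bias, type I error or inconsistency between documents. A reader might infer from the absence of a covariate that the primary test is invalid; randomisation and the simulations say otherwise.

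A reader might also infer that the D1 score is discarded. It is not, since it is the first point of the AUC in both branches. What is missing is adjustment for it.

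The size of the gain is open to challenge too. The larger gains need a correlation of about 0.5, which the documents do not supply, and every power figure rests on an effect size solved backwards from a sample-size statement without an SD. That also stands, and so the result is given as a range.

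Finally, SAP 12 shows that diary answers had been examined when the plan was written, so a late change to the only conclusive test could invite doubt about prespecification. This is a real cost. It can be contained only if the change is dated before unblinding.

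**Conclusion.** The point holds as an efficiency improvement of undetermined size. Neither branch of the primary test adjusts for a pre-treatment score that every analysed subject has. At the implied effect size and 90 per group, the gain in power from ANCOVA in the t-test branch is about 1 point at a correlation of 0.2, 3 points at 0.3 and 9 points at 0.5. The rank counterpart gains similar amounts in the lognormal case examined. These figures assume the back-solved effect, the stated alpha and the chosen correlations.

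Two stronger readings are not supported. One is that the trial certainly loses a material amount of power: at a correlation of 0.2 or less the gain is 0 to 1 points. The other is that rank ANCOVA is generally better than raw-scale ANCOVA: it is for the lognormal shape, but the reverse holds for the gamma shape, and the documents do not say which shape applies.

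**What to change.** Before unblinding:

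1. **t-test branch.** Use ANCOVA of AUC(D1–D8) on treatment, with the D1 total WURSS-21 score as covariate. Name the on-site V1 entry as the D1 value, because protocol 7.4.1 also lists an evening diary under D1–D8.
2. **Wilcoxon branch.** Use its rank counterpart: rank of AUC on treatment and rank of the D1 score.
3. **Choice of branch.** State one normality rule in advance. The SAP names none.
4. **Sensitivity.** Keep the unadjusted t-test and Wilcoxon test as sensitivity analyses.
5. **Estimate.** Report the ANCOVA-adjusted mean difference with a two-sided 90% confidence interval, which matches the one-sided 0.05 test in the t-test branch. In the rank branch, label it as descriptive, because it does not correspond to the rank test.
6. **Sub-scores.** Adjusting each sub-score AUC for its own D1 value is optional, since those p-values are for information only.

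The change needs no new data, visits or subjects, and little programming. Its real cost is a documented change to the primary test: an amendment under protocol section 10, or a reported deviation under protocol 8.10, with an entry in SAP 12. The blind review meeting in protocol 9.3, which validates the SAP, is a natural place to date it. If unblinding has occurred, or the sponsor keeps the primary test, add the adjusted analysis as a labelled sensitivity analysis only; the precision of the primary test then stays as planned.

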### 10.2. Analysis of the secondary efficacy criteria

#### 10.2.1. AUC for each of the WURSS-21 components (symptoms and Quality-of-Life)

For the symptoms' and Quality-of-Life's scores of the WURSS-21 questionnaire, the AUC will be computed by the method described in §6.4.7 and a t-test (or a Wilcoxon test if the normality assumption is not acceptable) will be performed on the means of AUC during first eight days of symptoms between treatment groups.

The symptoms' WURSS-21 score at each time point is the sum of the items 2 to 11 of the WURSS-21 questionnaire:

$$\text{At each time point } t: \text{WURSS}_{\text{symptoms}}(t) = \sum_{j \in \{2; \dots; 11\}} \text{WURSS}_j(t)$$

The Quality-of-Life's WURSS-21 score at each time point is the sum of the items 12 to 20 of the WURSS-21 questionnaire:

$$\text{At each time point } t: \text{WURSS}_{\text{QoL}}(t) = \sum_{j \in \{12; \dots; 20\}} \text{WURSS}_j(t)$$

At time points the questionnaire has been completed, possible unanswered items will be imputed by the method described in §6.4.6.

Subjects will be analysed on the Full Analysis Set and the Per-Protocol Set. In each case, boxplots of both AUC on symptoms' and Quality-of-Life's scores will be realized by treatment group. Numbers of available data and p-values will be printed on the figure.

#### 10.2.2. Impact of the treatment on the cold symptoms' duration

Hereinafter, the “recovery date” is the first day of two last days the patient answered to the WURSS-21 questionnaire. The patient must have reported a negative answer to the question 1 (“not sick”) and the two last days must be consecutive. Otherwise, there is no “recovery date” for the patient.

For the items 2 to 11 of WURSS-21 questionnaire, the duration of the corresponding symptom is defined as the duration between first symptomatic day and last symptomatic day.

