**D1-D8 (at home):**

The patient will be asked to complete the electronic diary daily (WURSS-21 assessed once daily in the evening, taking into account the symptoms from the morning to the evening, adverse events/incidents/expected undesirable side effects and concomitant medications).

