**Visit 2 (V2) – (Day 13-15): end of study**

The investigator or his/her delegated designee will:

- Perform a physical and clinical examination. A pharyngeal nasal swab will be performed by the investigator or by the delegated study nurse to check for absence or presence of SARS-CoV2.
- Validate adverse events pertinent in the context of the common cold and of additional study procedures /incidents linked to medical device use and concomitant medications reported in the e-diary and complete the e-CRF accordingly and report any new relevant safety events.
- Ask the patient to complete the WURSS-21 if he/she still has symptoms.
- Assessed the compliance to the treatment by weighting the device returned by the subject. In case of nasal spray dysfunction and attribution of a new treatment using the back-up randomization list, the compliance will be assessed by weighting both devices. If a nasal spray is lost, the investigator will ask the patient to specify the number of missed nasal spray use and will report the data into the e-CRF.
- Ask the patient to complete a satisfaction questionnaire.

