**Cold symptom's duration (days) = Last symptomatic day – first symptomatic day + 1**

For a given symptom, a symptomatic day is a day the patient gave an answer other than negative to the corresponding question (“do not have this”). Missing answers will be imputed by the LOCF.

The considered symptomatic days are between D1 and either D15, or the end of the study, or the day before the recovery date, whichever occurs first. Symptomatic days from the recovery date will not be taken into account.

For each of the items 2 to 11 of the WURSS-21 questionnaire, the origin date will be the date of the first symptomatic day.

The considered event is the end of the symptom.

For patients who reported a negative answer to the corresponding question on the last day they answered to it, or for patients with a recovery date, the event date will be the last symptomatic day before his/her last day of completion of the questionnaire, or before the recovery date if it exists.

Patients who did not report a negative answer to the corresponding question on the last day they answered to it, and without recovery date, will be censored at D15 or at the end of the study, and the censoring date will be the date of D15 or the reference end date, whichever occurs first.

For patients who never reported the presence of a given symptom (never ticked “very mild”, “mild”, “moderate” or “severe”) and having completed the questionnaire at D1, the origin date for the symptom will be D1, the symptom will be censored at D1 and the corresponding duration will be zero. If patients who never reported the presence of a given symptom did not complete the questionnaire at D1, neither origin date nor censoring date will be defined for this symptom and the corresponding duration will be missing.

For each of the items 2 to 11 of the WURSS-21 questionnaire, duration endpoints will be summarized using the medians, with 95% confidence intervals (CIs) for the medians by group. Results for Healsea® Rescue\* group and Placebo group will be compared using Wilcoxon-Mann-Whitney test. Subjects will be analysed on the FAS.

For each duration, boxplots will be realized by treatment group. Numbers of available data and p-values will be printed on the figure.

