## 12. CHANGES IN THE CONDUCT OF THE STUDY OR PLANNED ANALYSIS

The cold symptoms' duration was defined in the protocol as the number of symptomatic days between D1 and the first day the subject reports not having the symptom for two consecutive days.

Furthermore, since several patients still reported having symptoms while they reported they did not feel sick anymore at the question 1 during the two last days of completion of the WURSS-21 questionnaire, their positive answers to the cold symptoms' items have been considered as non-significant. Consequently, the question 1 has been taken into account instead of the corresponding items to determine the end of the cold symptoms' duration, however only on the condition that the two last days of completion were consecutive.

If the two last days of completion were not consecutive, positive answers to cold symptoms' items are still considered as symptomatic, even if the two last answers to the question 1 are negative. The symptom ends at the last symptomatic day if the patient reported the absence of this symptom after this day. Otherwise, the duration of the symptom is censored at D15 or at the end of the study, whichever occurs first.

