### 13.3. WURSS-21 questionnaire – Daily symptom report

Please complete the WURSS -21 in **the evening**, taking in account the symptoms from the morning to the evening, until you do not feel sick during two consecutive days (first question ticked NO during 2 consecutive days). In the case you already ticked “not sick” for 2 consecutive days during the TREATMENT PERIOD (D1 to Day 8), please do not complete the questionnaire either.

Please fill in one circle for each of the following items:

	Not sick 0	Very mildly		Mildly		Moderately		Severely	
	0	1	2	3	4	5	6	7	
How sick do you feel today?	0	0	0	0	0	0	0	0	0

Please rate the **average severity of your cold symptoms over the last 24 hours** for each symptom:

	Do not have this symptom 0	Very mild		Mild		Moderate		Severe	
	0	1	2	3	4	5	6	7	
Runny nose	0	0	0	0	0	0	0	0	0
Plugged nose	0	0	0	0	0	0	0	0	0
Sneezing	0	0	0	0	0	0	0	0	0
Sore throat	0	0	0	0	0	0	0	0	0
Scratchy throat	0	0	0	0	0	0	0	0	0
Cough	0	0	0	0	0	0	0	0	0
Hoarseness	0	0	0	0	0	0	0	0	0
Head congestion	0	0	0	0	0	0	0	0	0
Chest congestion	0	0	0	0	0	0	0	0	0
Feeling tired	0	0	0	0	0	0	0	0	0

Over the last 24 hours, how much has your cold interfered with your ability to:

	Not at all 0	Very mildly		Mildly		Moderately		Severely	
	0	1	2	3	4	5	6	7	
Think clearly	0	0	0	0	0	0	0	0	0
Sleep well	0	0	0	0	0	0	0	0	0
Breathe easily	0	0	0	0	0	0	0	0	0
Walk, climb stairs, exercise	0	0	0	0	0	0	0	0	0
Accomplish daily activities	0	0	0	0	0	0	0	0	0
Work outside the home	0	0	0	0	0	0	0	0	0
Work inside the home	0	0	0	0	0	0	0	0	0
Interact with others	0	0	0	0	0	0	0	0	0

Live your personal life	0	0	0	0	0	0	0	0
-------------------------	---	---	---	---	---	---	---	---

**Compared to yesterday, I feel that my cold is...**

Very much better	Somewhat better	A little better	The same	A little worse	Somewhat worse	Very much worse
0	0	0	0	0	0	0

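### The SAP's recovery date follows the last two diary entries, so the duration of a symptom still ticked after the patient feels well depends on when the diary stopped or skipped a day

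*SAP*

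**What the plan says.** For items 2 to 11 of the WURSS-21, SAP 10.2.2 gives duration as "Last symptomatic day – first symptomatic day + 1". Days are counted only up to the day before the recovery date: "Symptomatic days from the recovery date will not be taken into account". That date "is the first day of two last days the patient answered to the WURSS-21 questionnaire". Item 1 must be 'not sick', and "the two last days must be consecutive"; otherwise the patient has no recovery date. Without one, an item that was positive on its last answer is censored at D15 or at the end of the study.

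SAP 12 gives the reason for using item 1: several patients reported symptoms while no longer feeling sick, and those answers were judged non-significant. It then makes an exception: "If the two last days of completion were not consecutive, positive answers to cold symptoms' items are still considered as symptomatic". The exception applies even when both of the last item 1 answers are negative.

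The documents differ on when the diary ends. On the form in SAP 13.3, the instruction "In the case you already ticked “not sick” for 2 consecutive days during the TREATMENT PERIOD (D1 to Day 8), please do not complete the" refers to the daily form itself. For D1-D8, Protocol 7.4.1 states "The patient will be asked to complete the electronic diary daily", and the Synopsis endpoints and Protocol 7.1.3 also schedule the WURSS-21 daily to D8.

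They differ on V2 as well. Protocol 7.4.1 (Visit 2) says "Ask the patient to complete the WURSS-21 if he/she still has symptoms". The Synopsis design section, the flow chart footnote, Protocol 7.1.4 and SAP 3 ask for it only if the patient has not already ticked 'not sick' on two days running.

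**The concern.** SAP 12 sets out to disregard symptoms ticked after the patient feels well. A cut-off tied to the end of the diary does so only when the diary ends on the second 'not sick' day. Each further completed day moves the recovery date one day later and lets in one more day of the symptoms that were meant to be ignored. A missed evening just before the last entry removes the recovery date altogether.

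The rule can also hide real differences. With a complete D1-D8 diary and an item positive throughout, a patient who is 'not sick' from D3 and one who is 'not sick' from D7 both get recovery date D7 and 6 days.

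Symptom duration is the first secondary objective in SAP 2.2. It is reported for ten items with medians, confidence intervals and p-values. Where symptoms outlast feeling sick, those results would partly reflect diary behaviour.

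**Working it through.** The documents give no figure for this point, so the check applies the SAP 10.2.2 rules to one illness under different diary patterns.

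**Inputs from the SAP**
- Recovery date R: the first of the last two answered days, if they are adjacent and item 1 is 0 on both; otherwise none.
- Days counted: D1 to R − 1, or to D15 or study end if sooner.
- Duration: last symptomatic day − first symptomatic day + 1.
- No R and last item answer positive: censored at D15 or study end. V2 falls on D13-D15.

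**Assumed illness:** item 1 above 0 on D1-D3 and 'not sick' from D4; one symptom item positive on every completed day from D1; no form at V2.

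| Diary pattern | Last two answered days | R | SAP duration (days) | Recovery from earliest two 'not sick' days |
|---|---|---|---|---|
| Stops D5 | D4, D5 | D4 | 3 − 1 + 1 = 3 | 3 |
| Stops D6 | D5, D6 | D5 | 4 − 1 + 1 = 4 | 3 |
| Stops D7 | D6, D7 | D6 | 5 − 1 + 1 = 5 | 3 |
| Stops D8 | D7, D8 | D7 | 6 − 1 + 1 = 6 | 3 |
| To D8, D7 skipped | D6, D8 | none | censored, 13-15 | 3 |
| Stops D4 | D3, D4 | none | censored, 13-15 | censored, 13-15 |
| D5 skipped, stops D6 | D4, D6 | none | censored, 13-15 | censored, 13-15 |

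**The 13-15 figure.** It takes the censoring date as the end of the interval: 13 − 1 + 1 = 13 to 15 − 1 + 1 = 15. Read literally, the duration formula uses the last symptomatic day, which for the skipped-D7 diary gives 8 − 1 + 1 = 8. The SAP does not say which value enters the Wilcoxon-Mann-Whitney test. On either reading the value differs from 3 and from 6.

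**Changing the assumption on the item**
- Item ends on D3, before the patient feels well: 3 days in every pattern.
- Item ends on D5: the SAP gives 3 (stops D5), 4 (stops D6) and 5 (stops D7, stops D8, or D7 skipped). The alternative rule gives 3 in all five patterns.

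**Protocol definition for comparison.** The protocol ends a symptom at the first two consecutive days without that symptom. If the item stays positive to V2, it is censored in every pattern. The dependence on the stopping day therefore comes from the SAP's change.

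**The case against.** The best defence is the form itself. If every patient stops after two consecutive 'not sick' days, the last two days are the first two 'not sick' days, and the SAP rule equals the proposed one. SAP 7.2 describes recovery in the same way, as two consecutive negative answers to item 1. This stands, but only if everyone follows the form, and the protocol's schedule runs daily to D8. SAP 7.2 treats a missing assessment at D8-1 as a major deviation and refers to daily calls about uncompleted questionnaires between D1 and D8. Those calls should make gaps less common, but they also encourage entries past the second 'not sick' day.

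Several stronger readings are tempting but not supported:
- That duration depends only on when the diary stopped. Two diaries that both end on D8 give 6 days or a censored value; the difference is the skipped D7.
- That the V2 questionnaire routinely removes the recovery date. Only the Visit 2 text in Protocol 7.4.1 asks for a form from any patient with symptoms. The other four places would require none from a patient who has already ticked 'not sick' twice running.
- That the protocol's figure of 75% with reduced or resolved symptoms within 7 days measures how many patients are affected. It does not show how many keep symptoms after feeling well.
- That the treatment comparison is biased. The trial is double-blind, and nothing in the documents shows that diary-keeping differs by arm.

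It is also fair to say that SAP 12 discloses the rule, and that SAP 6.3.1 makes all non-primary results descriptive, with p-values for information only.

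**Conclusion.** The point holds for items 2 to 11 that are still ticked after the patient reports 'not sick'. For one and the same illness the SAP gives 3, 4, 5 or 6 days according to the stopping day. It gives a censored value (13-15 days by censoring date, 8 by the literal formula) if the day before the last entry is skipped. This works against SAP 12's own reason for using item 1.

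These figures rest on the assumed course: 'not sick' from D4 and the item positive throughout. SAP 12 confirms that patients with residual symptoms exist but does not say how many, so the effect on group medians cannot be sized from the documents. Added noise is the supported consequence; bias between arms remains only a possibility. Symptoms that end before the patient feels well are unaffected, and the primary AUC does not use the recovery date. The change is worth making, but the trial's main conclusion does not depend on it.

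**What to change.** In SAP 10.2.2 and 12, define the recovery date as the first day of the earliest two consecutive calendar days with item 1 'not sick' that is not followed by a later item 1 above 0. State that it does not depend on the last completion date, on later gaps or on any form completed at V2. The patterns stopping at D5 to D8 and the skipped-D7 pattern then all give 3 days.

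State also which value a censored duration takes in the Wilcoxon-Mann-Whitney test and in the medians.

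Reconcile the stopping instruction in SAP 13.3 with the daily D1-D8 schedule in the Synopsis and Protocol 7.1.3 and 7.4.1. Reconcile the V2 condition in Protocol 7.4.1 with the Synopsis, the flow chart, Protocol 7.1.4 and SAP 3.

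The cost is about two sentences on the recovery date, one on censoring and one changed derivation, with no new data. The limit is that patients who never record two consecutive 'not sick' days, with the item positive at their last answer, stay censored under either rule; their number should be reported by arm.
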